Study Protocol and Statistical Analysis Plan

Study Title: Long Duration Activity and Metabolic Control After Spinal Cord Injury

NCT03139344

Document Version: 11/3/2022

Study Objectives

Skeletal muscle is the largest endocrine organ in the body, playing an indispensable role in glucose homeostasis. Spinal cord injury (SCI) prevents skeletal muscle from carrying out this important function. Dysregulation of glucose metabolism precipitates high rates of metabolic syndrome, diabetes, and other secondary health conditions (SHCs) of SCI. These SHCs exert a negative influence on health-related quality of life (HRQOL). New discoveries support that a low level of activity throughout the day offers a more effective metabolic stimulus than brief, episodic exercise bouts.

The **purpose** of this study is to translate this emerging concept to the population of individuals with SCI by using low-force, long-duration electrical muscle stimulation to subsidize daily activity levels. The **long-term goal** of this research is to develop a rehabilitation strategy to protect the musculoskeletal health, metabolic function, and health-related quality of life of people living with complete SCI.

Specific Aim 1: To compare acute changes in skeletal muscle gene regulation in individuals who receive a single session of low frequency (LF) or high frequency (HF) exercise.

Hypothesis 1: The expression of genes regulating skeletal muscle metabolism will support that HF and LF both initiate a shift toward an oxidative muscle phenotype.

Specific Aim 2: To compare changes in skeletal muscle gene regulation and systemic biomarkers of metabolic health in individuals with SCI who receive LF or HF for 6 months.

Hypothesis 2: LF and HF will both yield gene expression changes indicating a shift toward a slow-oxidative muscle phenotype.

Hypothesis 3: LF training will yield systemic biomarker changes indicating improved glucose homeostasis and reduced systemic inflammation.

Specific Aim 3: To measure subject-reported HRQOL using the PROMIS survey metric.

Hypothesis 4: LF training will yield improved self-reported QOL via PROMIS physical and mental health scales.

Design

Population: Individuals with motor-complete spinal cord injury (SCI) (AIS A – B), 21 to 60 years of age.

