Exclusion Criteria: Pressure ulcers, chronic infection, lower extremity muscle contractures, deep vein thrombosis, bleeding disorder, recent limb fractures, any comorbid disease known to affect bone metabolism (such as parathyroid dysfunction), pregnancy, anti-osteoporosis medications, Vitamin D supplements, Metformin or other medications for diabetes

Enrollment: Non-random assignment

Study Arm 1: Acute gene regulation in response to a single session of low frequency electrically induced exercise

Study Arm 2: Acute gene regulation in response to a single session of high frequency electrically induced exercise

Study Arm 3: Adaptations in gene regulation, systemic metabolic markers, and patient-report metrics in response to training with low frequency electrically induced exercise

Study Arm 4: Adaptations in gene regulation in response to training with high frequency electrically induced exercise

Study Arm 5: Comparator participants will undergo selected outcome measures to provide comparison values for Experimental arms.

Methods

Baseline Characteristics: Participants will provide information on age, sex, race, ethnicity, and level of SCI (quadriplegia, paraplegia)

Study Arms 1 and 2: Participants will undergo unilateral vastus lateralis skeletal muscle biopsy: they will be positioned in supine, the skin over the biopsy site will be sterilized, up to 3 mL of 1% lidocaine will be injected locally, and a 1/8th inch incision will be made with a scalpel. The biopsy needle will then be inserted and four cores of muscle (~ 20 mg) will be obtained from four passes of the needle through the same puncture site. The incision site will be closed with steri-strips or a butterfly bandage and the subject will be told not to perform electrical muscle stimulation or wet the area for 48 hours. Muscle specimens will be immediately processed for microarray analysis. Participants will then undergo a single session of electrically-induced low frequency (Arm 1) or high frequency (Arm 2) exercise to the quadriceps and hamstrings muscles of the non-biopsied limb. Stimulating electrodes will be placed over the quadriceps and hamstrings muscles, and electrical stimulation will be given to induce an isometric closed kinetic chain knee extension moment. Participants will rest for 3 hours and then the vastus lateralis biopsy procedure will be repeated on the limb that performed electrically-induced exercise.

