Study Arm 3: Participants will complete a baseline assessment including the biopsy procedure described above, completion of the PROMIS self-reported quality of life survey, and venipuncture. Venous blood will be collected into vacutainer tubes with anticoagulant for glucose, kept on ice in dark conditions. The

blood will be centrifuged and analyzed with a blood auto-analyzer. After two weeks, participants will begin low frequency electrically induced exercise training. They will perform electrically induced exercise as described above for 6 months. At the conclusion of training, participants will undergo repeat biopsy, PROMIS survey, and venipuncture.

Study Arm 4: Participants will complete a baseline muscle biopsy assessment using the procedure described above. After two weeks, participants will begin high frequency electrically induced exercise training. They will perform electrically induced exercise as described above for 6 months. At the conclusion of training, participants will undergo repeat biopsy.

Study Arm 5: Comparator participants will complete the PROMIS self-reported quality of life survey.

Outcome Measures: Microarray will be used to measure mRNA transcription levels for genes that regulate cellular adaptation to exercise (peroxisome proliferator-activated receptor gamma coactivator alpha – PGC1-alpha), muscle oxidative metabolism (pyruvate dehydrogenase kinase – PDK4, actin binding Rho activating protein – ABRA, and nuclear receptor subfamily 4 group A member 3 – NR4A3), and muscle fiber type (myosin heavy chain 6 – MYH6, myosin light chain 3 – MYL3, myosin heavy chain 7 – MYH7, actin 3 – ACTN3).

Standard clinical assays will be used to measure levels of serum biomarkers for metabolic control (fasting insulin, fasting glucose, fasting glucose-insulin ratio, fasting hemoglobin A1c) and systemic inflammation (c-reactive protein – CRP).

For the PROMIS participant-report metric of health-related quality of life, raw scores will be used to calculate the physical health t-scale and the mental health t-scale.

Statistical Analysis Plan

Gene mRNA transcript levels will be expressed as Log_2 intensity (arbitrary units). Each blood biomarker will be expressed as its commonly-used clinical unit of measure (eg. mg/dL). PROMIS physical and mental health scores will be expressed as t-scores, which are anchored to the U.S. population mean (50) and standard deviation (10).

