Change over time for each gene-related outcome measure will be assessed via one-way ANOVA. For study Arms 1 and 2, gene expression levels from the baseline biopsy will be contrasted to the 3 hour post-exercise biopsy. For study Arms 3 and 4, gene expression levels from the pre-training biopsy will be contrasted to the post-training biopsy.

For study Arm 3, change over time in pre-training and post-training values for systemic biomarkers and for PROMIS scores will be assessed via 2-sided t-tests.

Pre-training values for PROMIS scores in study Arm 3 will be contrasted with the comparator cohort (study Arm 5) via 2-sided t-tests.

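### The per-gene one-way ANOVA has no participant term and uses only each gene's own variance; a participant-blocked model, moderated across the array if arms are small, would be more efficient.

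*Combined protocol and SAP*

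**What the plan says.** The Statistical Analysis Plan gives one sentence on method for the gene outcomes: "Change over time for each gene-related outcome measure will be assessed via one-way ANOVA". It then defines the contrasts. For the acute arms: "For study Arms 1 and 2, gene expression levels from the baseline biopsy will be contrasted to the 3 hour post-exercise biopsy". For the training arms: "For study Arms 3 and 4, gene expression levels from the pre-training biopsy will be contrasted to the post-training biopsy". In both cases the two biopsies come from the same participants; in Arms 1 and 2 they come from opposite limbs (Methods, Study Arms 1 and 2).

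The Outcome Measures paragraph says "Microarray will be used to measure mRNA transcription levels for genes that regulate cellular adaptation to exercise", and goes on to oxidative-metabolism and fibre-type genes. Eight genes are named in all, and levels are analysed on the log2 scale.

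Hypothesis 1 ("HF and LF both initiate a shift toward an oxidative muscle phenotype") and Hypothesis 2 ("LF and HF will both yield gene expression changes indicating a shift toward a slow-oxidative muscle phenotype") rest on these gene outcomes, and no other test of them is planned.

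The documents mention no participant term, repeated-measures structure or sharing of variance across genes. They state no arm size, significance level, power, SD or effect size. They do not say how many other genes the array reads or whether those readings are kept.

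**The concern.** Two sources of precision appear to go unused.

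- **Pairing.** A plain one-way ANOVA treats the before and after specimens as independent groups. If a participant's two readings are positively correlated, the between-participant variation stays in the error term. The test is then conservative and loses power.
- **The rest of the array.** Even with pairing handled, each test estimates its error variance from one gene in one arm, on n−1 degrees of freedom. A microarray ordinarily returns readings for many other genes on the same specimens. Empirical-Bayes moderation uses their variances to stabilise each gene's own and adds prior degrees of freedom.

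At stake is the chance of detecting the changes that Hypotheses 1 and 2 predict, from tissue obtained by repeat biopsy.

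**Working it through.** **Inputs.** From the documents: one-way ANOVA per gene, two time points within each arm, microarray, log2 scale, eight genes. The plan has no stated figure to reproduce. Everything else is assumed: two-sided 5%; n pairs per arm from 4 to 20; gene variances following a scaled inverse chi-square distribution with typical variance s0² and prior degrees of freedom d0 = 4 (2 and 8 as a range). The power and error figures below are simulated, with at least 100,000 draws per setting.

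**Step 1: pairing.** Let σ² be the variance of a single reading and ρ the within-participant correlation. The mean change has true variance 2σ²(1−ρ)/n, but the unpaired test works with 2σ²/n. At ρ = 0.5 and n = 6 these are 2 × 0.5/6 = 0.17σ² and 2/6 = 0.33σ², so the unpaired test uses twice the true variance. Its type I error is then about 1.3%, and power for a 1.0 SD change is about 32%, against 51% paired.

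The result depends on ρ. At n = 6, with a change sized to give the unpaired test 50% power at ρ = 0:

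| ρ | Unpaired power | Paired power |
|---|---|---|
| 0 | 50% | 42% |
| 0.3 | 50% | 55% |
| 0.5 | 51% | 69% |
| 0.7 | 52% | 88% |

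**Step 2: moderation, given pairing.**

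- Ordinary paired test: t = mean change / (s/√n) on n−1 df.
- Moderated test: replace s² by (d0·s0² + (n−1)·s²)/(d0 + n−1), on d0 + n−1 df.

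At n = 5 and d0 = 4 the weights are 4/8 and 4/8. The df rise from 4 to 8, and the critical value falls from 2.776 to 2.306.

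Average power over genes, ordinary then moderated, d0 = 4:

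| Pairs | Change of 1.0 typical SD | Change of 1.5 typical SDs |
|---|---|---|
| 4 | 28% → 36% | 48% → 68% |
| 5 | 38% → 46% | 62% → 76% |
| 8 | gain about 6 points | 82% → 88% |
| 12 | – | 91% → 93% |
| 20 | gain 2 points or less | gain 2 points or less |

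At n = 5 and 1.5 SDs, the result is 55% → 65% with d0 = 2 and 66% → 84% with d0 = 8. Type I error averaged over genes is 5% for both tests throughout.

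**Step 3: one particular gene.** The 5% for the moderated test is an average. Set s0² = 1, n = 5 and d0 = 4.

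- True variance 4: the moderated variance averages (4×1 + 4×4)/8 = 2.5, which is too small. Type I error is about 11% (about 9% at n = 8).
- True variance 0.25: it averages (4×1 + 4×0.25)/8 = 0.625, which is 2.5 times too large. Power for a change of 1.5 of the gene's own SDs falls from 71% to 39% (95% to 85% at n = 8).
- True variance 0.5: there is no gain (71% and 70%).

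The ordinary paired test stays at 5% for every gene variance tried.

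**The case against.** The strongest reply is that nothing here is an error. Once paired, an ordinary test of eight named genes is valid, so moderation is an efficiency preference. That stands.

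It can also be said that one-way ANOVA applied to change over time is shorthand for a repeated-measures analysis. That is possible, but the text does not say so, and one added phrase would settle it.

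The eight genes were chosen in advance and are not a random draw from the array. A power gain averaged over exchangeable genes therefore does not establish a gain for these eight, and the documents give no gene variances. This stands and limits the claim.

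The moderation gain also depends on the baseline. Against the unpaired test as written (2n−2 df), with d0 from 2 to 10 and an effect sized to give the ordinary test 50% power at the typical variance, it is 3 to 9 points at n = 4, 1 to 4 at n = 6 and at most 1.6 at n = 10. The larger gains in the table apply once pairing is in place. At moderate correlation, pairing usually matters more.

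A reader might go further and infer that unstable per-gene variances produce excess false positives. They do not: the t and F reference distributions already allow for a poorly estimated variance, and the ordinary paired test holds 5%. Nor is the gain free of assumptions, as the results for atypical genes show.

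**Conclusion.** The point holds as an inexpensive efficiency improvement. The plan's wording leaves out the participant term. Whether adding it raises power depends on the correlation: at 6 pairs it loses power at zero correlation and gains from about 0.3 upward in the settings above. It is still the analysis that matches the design.

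The further gain from moderation is worth having only if arms are small, roughly 10 to 12 pairs or fewer, and is negligible by 20. Small arms are an inference from the population and the repeat biopsies, since no sample size is stated. Availability of whole-array data is likewise inferred from the word microarray; the eight named genes alone are too few to estimate a prior variance well.

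All magnitudes rest on the assumed correlation, effect sizes and prior degrees of freedom. The robust prior was not simulated, so it has not been shown to remove the distortion for atypically variable genes.

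**What to change.** In the Statistical Analysis Plan:

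1. Replace the per-gene one-way ANOVA with a linear model on log2 intensities with participant as a blocking term.
2. State the number of pairs per arm and whether whole-array data are retained.
3. If arms have roughly 10 to 12 pairs or fewer and the whole-array data are kept, fit the model to all probes with empirical-Bayes variance moderation and a robust prior.
4. Report the eight named genes as log2 fold change with 95% CI, beside the ordinary paired result. Flag any gene that is significant only under moderation.
5. State the limitation: the 5% error rate under moderation holds on average over genes, and a gene with atypically high or low variance can depart from it in either direction.

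The cost is a few sentences and standard software, with no new participants or biopsies. Moderation does not deal with multiplicity across the eight genes, which needs its own statement.

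### The only analysis that uses Arm 5 is an unadjusted t-test between non-randomised groups, so a PROMIS difference could reflect age or sex mix (minor; cheap to improve)

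*Combined protocol and SAP*

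**What the plan says.** The Design section gives the allocation as "Enrollment: Non-random assignment" and describes Arm 5 as follows: "Comparator participants will undergo selected outcome measures to provide comparison values for Experimental arms". Methods narrows this to one measurement: "Study Arm 5: Comparator participants will complete the PROMIS self-reported quality of life survey". The Statistical Analysis Plan then uses Arm 5 once: "Pre-training values for PROMIS scores in study Arm 3 will be contrasted with the comparator cohort (study Arm 5) via 2-sided t-tests".

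Under Baseline Characteristics, Methods states: "Participants will provide information on age, sex, race, ethnicity, and level of SCI (quadriplegia, paraplegia". None of these variables has a role in the Statistical Analysis Plan. PROMIS results are expressed as T-scores on a single U.S. reference scale (mean 50, SD 10), with no age- or sex-specific norm mentioned.

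The only population stated is this one: "Population: Individuals with motor-complete spinal cord injury (SCI) (AIS A – B), 21 to 60 years of age". Arm 5 has no separate eligibility, source or SCI status. The one hypothesis about PROMIS concerns training: "Hypothesis 4: LF training will yield improved self-reported QOL via PROMIS physical and mental health scales".

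**The concern.** Randomisation would make age and sex differences between groups a matter of chance. Here there is none, and nothing in the design ties the age or sex mix of Arm 5 to that of Arm 3. The eligible range of 21 to 60 years leaves room for a real age gap. Rescaling every score to one national mean and SD moves both groups equally, so it cannot remove a difference caused by age or sex.

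A two-sided test also invites an inferential reading. If the groups differ in age or sex, and PROMIS scores vary with them, the test can show a difference that is only demographic, or hide or exaggerate a real one. At stake is the meaning of the baseline comparison that Arm 5 was added to provide.

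**Working it through.** The plan states no sample size, power, alpha or expected difference for this contrast, so there is no figure of its own to reproduce. What follows is an illustration of size.

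**Inputs**
- From the Statistical Analysis Plan: SD = 10 (U.S. reference value, taken as the within-group SD) and a two-sided test.
- Assumed: alpha 0.05; equal groups of 10, 20 or 40; a PROMIS slope of 0.1 to 0.2 points per year of age; a mean age gap of 5 to 15 years; a within-group age SD of 10 years, used only for the precision step.

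**Step 1: bias of the unadjusted difference.** Bias = slope × age gap.
- Low end: 0.1 × 5 = 0.5 points.
- High end: 0.2 × 15 = 3.0 points.
- No gap: 0 points.

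A second route gives the same range. Bias = r × d × SD, where r is the correlation of the covariate with PROMIS and d the imbalance in SD units. With r from 0.1 to 0.3 and d from 0.5 to 1.0, this runs from 0.1 × 0.5 × 10 = 0.5 to 0.3 × 1.0 × 10 = 3.0. This form applies to any covariate. No separate figure is offered for sex.

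**Step 2: false-positive rate when the groups differ only through the covariate.** The standard error is 10 × √(2/n), the noncentrality is bias divided by that standard error, and the rate comes from the noncentral t with 2n − 2 df. For n = 20 and a bias of 3: SE = 3.16, noncentrality = 3/3.16 = 0.95, critical t = 2.024 (38 df), rate = 15.2%.

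| Bias (points) | n = 10 per group | n = 20 per group | n = 40 per group |
|---|---|---|---|
| 0 | 5.0% | 5.0% | 5.0% |
| 0.5 | 5.1% | 5.3% | 5.6% |
| 1 | 5.5% | 6.1% | 7.3% |
| 2 | 7.1% | 9.5% | 14.3% |
| 3 | 9.7% | 15.2% | 26.3% |

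**Step 3: price of adjustment at 20 per group.** Adding two covariates moves the df from 38 to 36 and the critical t from 2.024 to 2.028, which is negligible. The larger cost is the overlap between group and age. The adjusted standard error is approximately 10 × √(2/n) × √(1 − r²) × √(1 + d²/4).
- r = 0.3, d = 1.0: 3.16 × 0.954 × 1.118 = 3.37.
- r = 0.2, d = 1.5 (slope 0.2, gap 15 years): 3.16 × 0.980 × 1.25 = 3.87.

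**Step 4: is the trade worthwhile?** Compare root mean squared errors at 20 per group and d = 1.5.
- r = 0.2 (bias 3.0): unadjusted √(3.16² + 3.0²) = 4.36, adjusted 3.87.
- r = 0.1 (bias 1.5): unadjusted √(3.16² + 1.5²) = 3.50, adjusted 3.93.

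Adjustment wins when age matters most. When age matters little it buys protection from bias at some cost in precision. This is a reason to report both estimates.

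**The case against.** The strongest reply is that the contrast is peripheral. It uses pre-training scores only, no hypothesis names it, and Hypothesis 4 is tested by the change within Arm 3. An unadjusted comparison of a cohort with comparators is also a legitimate prespecified description. This stands, and it keeps the point minor. The PROMIS values from Arm 5 also remain usable as descriptive comparison values, so it would be too strong to say that the arm fails its purpose.

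A reader might infer that the gap mixes the effect of SCI with age and sex. The documents do not support that. They never say that Arm 5 participants are free of SCI, and the only stated population has motor-complete SCI. If Arm 5 also has SCI, this is not a contrast of condition at all. The age and sex question remains under either reading.

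A reader might also take confounding as shown, or 26% as the expected error rate. Neither follows. Confounding is a risk whose size depends on an imbalance nobody has stated, and 26% needs both the largest assumed bias and 40 per group. A 15-year gap in mean age is large if both groups come from the 21 to 60 range, and a biopsy study may well have small groups, where the inflation is less.

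Finally, adjustment is not free, and it does not deal with unmeasured differences or an undefined comparator. With a large age gap it also leans on a linear age effect. All of this stands. It bears on how the model is reported and does not justify leaving age and sex out.

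**Conclusion.** The concern holds as a minor point. The sole Arm 5 analysis is unadjusted, the groups are not randomised, and neither design nor analysis controls for age or sex, which the plan intends to record. A difference in baseline PROMIS scores could therefore partly or wholly reflect demographic mix.

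Under the assumed slopes and age gaps the bias is 0.5 to 3.0 T-score points. The corresponding false-positive rates are about 5% to 10% at 10 per group, 5% to 15% at 20, and 6% to 26% at 40. These figures rest on assumed slopes, gaps, group sizes and alpha; only the SD of 10 and the two-sided test come from the plan. With balanced groups there is no bias and the rate is 5%. No conclusion about training changes.

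**What to change.** Replace the sentence on the Arm 3 versus Arm 5 contrast with the following content:
- The main analysis of each PROMIS scale is a linear model of the baseline T-score on group, age and sex. Injury level is added only if Arm 5 participants have SCI, since otherwise it has no value in that group.
- The adjusted difference is reported with its 95% CI, and the unadjusted difference is shown alongside.
- The SCI status of Arm 5 is stated, so that the contrast can be interpreted.
- The contrast is described as an observational comparison.

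The cost is a few sentences. No new data are needed if the Baseline Characteristics paragraph, which is not restricted by arm, covers Arm 5; this should be confirmed, because the Arm 5 paragraph in Methods mentions only the survey. Statistically, the model uses one residual degree of freedom per covariate and loses some precision when the groups are imbalanced. At 20 per group the standard error rises from 3.16 to about 3.4 at a 1 SD age gap and to about 3.9 at 1.5 SD. If the groups are small, keep to age and sex.
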